OCRPRO	Office of Clinical Research Policy and Regulatory Operations
OHRP	Office for Human Research Protections
PCR	polymerase chain reaction
PI	Principal Investigator
PLDS	post-Lyme disease syndromes
PTLDS	post-treatment Lyme disease syndrome
SAEs	serious adverse events
SBV	South Bay virus
SCID	Severe Combined Immunodeficiency
SMM	Sponsor Medical Monitor
SRCP	Safety Review and Communication Plan
UADEs	unanticipated adverse device effects
UPs	unanticipated problems
UPnonAE	unanticipated problem that is not an adverse event
US	United States

STATEMENT OF COMPLIANCE

The trial will be carried out in accordance with International Council for Harmonisation of Technical Requirements for Pharmaceuticals for Human Use (ICH) Good Clinical Practice (GCP) and the following:

- United States (US) Code of Federal Regulations (CFR) applicable to clinical studies (45 CFR Part 46, 21 CFR Part 50, 21 CFR Part 56, 21 CFR Part 312, and/or 21 CFR Part 812)

NIH-funded investigators and clinical trial site staff who are responsible for the conduct, management, or oversight of NIH-funded clinical trials have completed Human Subjects Protection and ICH GCP Training.

The protocol, informed consent form(s), recruitment materials, and all participant materials will be submitted to the Institutional Review Board (IRB) for review and approval. Approval of both the protocol and the consent form must be obtained before any participant is enrolled. Any amendment to the protocol will require review and approval by the IRB before the changes are implemented to the study. In addition, all changes to the consent form will be IRB-approved; an IRB determination will be made regarding whether a new consent needs to be obtained from participants who provided consent using a previously approved consent form.

PRÉCIS

Lyme disease is the most common vector borne disease in the United States. Although antibiotic therapy is clinically effective in treating the symptoms of Lyme disease for most patients early in the course of disease, a significant number of patients who receive therapy report persistent symptoms. The cause of persistent symptoms after antibiotic therapy for Lyme disease is an area of great controversy. Recent studies have shown that the organism (*Borrelia burgdorferi*) may persist in animals after antibiotic therapy and can be detected by using the natural tick vector (*Ixodes scapularis*) to acquire the organism through feeding (xenodiagnosis). Whether this occurs in humans is unknown. Currently available tests for human Lyme disease do not allow determination of persistent infection after antibiotic therapy.

We performed the first study of the use of *I. scapularis* larva for the xenodiagnosis of *B. burgdorferi* infection in humans. Our pilot study showed that xenodiagnosis was well tolerated with no severe adverse events (AEs). The most common AE was mild itching at the site. In this small pilot study, xenodiagnosis for *B. burgdorferi* was positive in 2 participants and indeterminate in 2 participants. Further studies are needed to determine the sensitivity of xenodiagnosis in evaluating the infection status of Lyme disease patients.

In this proposal, we want to further investigate the utility of xenodiagnosis for identifying persistence of infection with *B. burgdorferi* in treated human Lyme disease. Our objectives include assessing the link between detection of *B. burgdorferi* by xenodiagnosis and persistence of symptoms in patients diagnosed with Lyme disease, within 1 year, post therapy; compare the rate of detection of *B. burgdorferi* by xenodiagnosis after therapy in participants with post-treatment Lyme disease symptoms; identify subject characteristics related to the likelihood of detecting *B. burgdorferi* by xenodiagnosis including: time from infection, time between infection and therapy, time from therapy; and continue to assess the safety of xenodiagnosis in humans.

The results of study have the potential to resolve this long-standing controversy in Lyme disease pathogenesis. While xenodiagnosis is unlikely to be widely used in clinical practice due to the labor intensity and speed of testing, if our study shows a linkage between positive xenodiagnostic testing and persistence of symptoms after *B. burgdorferi* infection, it may prove to be a useful tool for testing new strategies for treatment and for correlation with more generally applicable diagnostic markers. Understanding the pathogenesis of persistent symptoms following Lyme disease, and identifying reliable diagnostic tests for determining the success of antibiotic therapy, is critical to the medical management of these patients.

1 BACKGROUND

Lyme disease is the most common vector borne disease in the United States ¹. It is transmitted to humans via the bite of infected *Ixodes* ticks. At the tick bite site, *Borrelia burgdorferi*, the causative organism of Lyme disease, enters the skin, often resulting in the characteristic erythema migrans (EM) rash. From the original entry site, the organism spreads to distant locations affecting the heart, joints and central nervous system. Many studies have shown that Lyme disease is treated successfully with antibiotics in the majority of cases, and patients with objective evidence of treatment failure are rare with currently recommended regimens ²⁻⁵. Patients with late manifestations can have a slower response to therapy, sometimes taking weeks or months to recover ⁶⁻¹⁴.

A portion of patients treated for Lyme disease will have persistent or relapsing non-specific symptoms (such as fatigue, musculoskeletal pain, and cognitive complaints) after receiving an adequate course of antibiotic therapy, a condition that is called post-Lyme disease syndrome. The best estimates of the prevalence of post-Lyme disease syndrome come from studies of patients with erythema migrans who received appropriate antibiotic treatment. 10-40% of such patients have persistent or intermittent subjective symptoms of mild to moderate intensity 12 months after completion of therapy ^{3,4,15-19}. The most common post-Lyme disease symptoms are fatigue, arthralgias, myalgias, headache, neck stiffness, paresthesias, sleeplessness, irritability, and difficulty with memory, word finding, and concentration ^{3,4,15-18}. The appearance of post-Lyme disease symptoms seems to correlate with disseminated disease, a greater severity of illness at presentation, and delayed antibiotic therapy ^{3,20-24}. The pathogenesis of these symptoms (whether due to persistent infection, immunologic dysfunction, or other mechanism) remains an area of great controversy.

A major concern has been that the symptoms of post-Lyme disease syndrome may represent persistent infection with *B. burgdorferi*. Hunfeld *et al.* ²⁵ reported a 50% recovery rate of *B. burgdorferi* from erythema migrans skin biopsies done before therapy in 3,421 patients, and 1.7% of skin biopsies of patients (19 out of 1148) remained *B. burgdorferi* positive by culture 2 months (range 1.3-3 months) after antibiotic therapy. Spirochete persistence was not accounted for by the development of resistance to the antibiotic. Objective evidence of *Borrelia* infection in patients with post-Lyme disease syndrome has not been found using polymerase chain reaction (PCR) ^{26,27} or culture ^{26,27}. It should be noted, however, that *B. burgdorferi* culture and PCR have low sensitivity in most body fluids from patients with Lyme disease ^{28,29}. Other tests that have not been helpful in evaluating patients with post-Lyme disease syndrome include changes in C6 antibody levels ³⁰ and antibodies in immune complexes ³¹. Current serologic testing for antibodies to *B. burgdorferi* remains positive for years after therapy and declines very slowly making it essentially useless for confirmation of successful therapy. There are many anecdotal reports of patients with different persistent symptoms improving with prolonged antibiotic therapy (and worsening with cessation), but randomized controlled trials to date have not shown significant, sustained benefit from antibiotic therapy ^{26,27,32}. The question of whether patients continue to harbor *B. burgdorferi* after antibiotic therapy has become a very contentious issue ³³.

Although the prevailing belief in the scientific and medical establishments is that patients do not continue to harbor *B. burgdorferi* and that long-term antibiotics are of no value, recent animal

data suggest that eradication of *B. burgdorferi* by antibiotics may not be complete. Studies in dogs, mice and non-human primate have shown that *B. burgdorferi* DNA can be detected in tissues for extended periods after antibiotic therapy³⁴⁻⁴⁰. Though positive testing for *B. burgdorferi* DNA by PCR has been used for diagnosis of the infection^{41 42 43,44}, it must be noted that PCR has the potential to recognize DNA from dead or dying bacteria⁴⁵.

Obtaining tissue samples of heart, joint, or bladder for testing would not be feasible as a diagnostic test in humans. *Ixodes* ticks feeding on antibiotic treated animals were able to acquire *B. burgdorferi* during their blood meal³⁴. The organism could be detected by PCR of the tick and could also be transmitted to immunodeficient SCID mice by the ticks during their next blood meal. These studies have now been replicated by other groups both in mice and in monkeys.^{38-40,46,47}

The use of a natural vector (i.e., *I. scapularis*) to detect the presence of an organism is called xenodiagnosis. Xenodiagnosis has been used in the diagnosis of human infections in instances where other diagnostic testing is difficult either due to difficulties/risks of obtaining proper specimens for testing or due to difficulty in cultivating the organism. Xenodiagnosis has long been used in Lyme disease research to provide definitive evidence of a host's infection status. For Lyme disease, tick saliva has been shown to be a chemoattractant for the organism and thus feeding ticks have the potential to aggregate and concentrate bacteria from a wide area, improving sensitivity⁴⁸.

Xenodiagnosis by feeding uninfected ticks on patients after antibiotic therapy could offer a minimally invasive method for determining the persistence of *B. burgdorferi* after antibiotic therapy. We have performed the first study of the use of *I. scapularis* larva for the xenodiagnosis of *B. burgdorferi* infection in humans. The primary goals of this study were to develop procedures that could be used in xenodiagnostic testing of patients after antibiotic therapy with Lyme disease and to determine the safety of tick xenodiagnosis in humans.

We have performed xenodiagnosis in 43 individuals. Xenodiagnosis has been well tolerated with no severe AEs. The most common AE was mild itching at the tick attachment site. Results from the initial 36 participants are described in our manuscript “Xenodiagnosis to detect *Borrelia burgdorferi* infection: A first-in-human study”, which has been published in the *Clinical Infectious Diseases* journal⁴⁹.

Participants who underwent xenodiagnosis included 10 patients with high C6 antibody levels, 10 patients with post-treatment Lyme disease syndrome (PTLDS), 5 patients with acute erythema migrans after completion of antibiotic therapy, one patient with erythema migrans on therapy (who also underwent xenodiagnosis after antibiotic therapy), and 10 healthy volunteers. Seven patients underwent more than one xenodiagnosis procedure.

As no previous protocol for xenodiagnosis with *I. scapularis* larva in humans existed, we developed a retention dressing using the LeFlap™ (Monarch Labs, Irvine, CA) dressing, which was modified for use with ticks. Participants enrolled early in the trial had fewer ticks feed successfully due to issues with the tick retention dressing that resulted in entrapment of the ticks in the adhesive.

After modifying the dressing by adding a foam ring to create a barrier between ticks and adhesive, we were more consistently able to get between 30 and 50% of ticks to feed successfully.

Xenodiagnosis was well tolerated. All participants successfully completed the tick placement and there were no withdrawals during the study. The most common AE was mild itching at the site, which was seen in 58% of participants, with a median duration of 3 days. Repeat of the xenodiagnosis procedure was similarly well tolerated, with mild itching at the site as the most common complaint. There were no serious AEs associated with the procedure. Although not a primary goal of this pilot study, we did find 2 participants that tested positive and 2 participants who tested indeterminate for the presence of *B. burgdorferi* in the xenodiagnostic ticks.

In this Phase 2 study, we plan to expand our study of xenodiagnosis for Lyme disease in humans. Xenodiagnostic evidence that *B. burgdorferi* survives in humans after antibiotic therapy may fundamentally change the approach to patients with persistent symptoms and provide physicians and researchers with a new tool with which to study the mechanisms of disease.

2 STUDY OBJECTIVES

1. Objective #1:
Assess the link between detection of *B. burgdorferi* by xenodiagnosis and persistence of symptoms in patients diagnosed with Lyme disease, within 1 year, post therapy.
2. Objective #2:
Compare the rate of detection of *B. burgdorferi* by xenodiagnosis after therapy for Lyme disease in participants with symptoms of post-treatment Lyme disease.
3. Objective #3:
Identify subject characteristics related to the likelihood of detecting *B. burgdorferi* by xenodiagnosis including: time from infection, time between infection and therapy, time from therapy.
4. Objective #4:
Continue to assess the safety of xenodiagnosis in humans.

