3.2 Inclusion Criteria

Criteria for the diagnosis and therapy for Lyme disease can be found at “The clinical assessment, treatment, and prevention of Lyme disease, human granulocytic anaplasmosis, and babesiosis: clinical practice guidelines by the Infectious Diseases Society of America”⁵.

Patients with Lyme disease, post-therapy (N=100)

1. Age 18 or older.
2. Lyme disease diagnosed in the previous 13 months, fulfilling the case definition of confirmed or probable Lyme disease by the US Centers for Disease Control and Prevention (CDC) <https://www.cdc.gov/nndss/conditions/lyme-disease/case-definition/2017/>.
3. Completion of 1 course of antibiotics at least 3 months and up to 12 months between the end of the therapy and the xenodiagnostic procedure.
4. Antibiotic treatment fulfills the Infectious Diseases Society of America guidelines for the recommended therapy for Lyme disease⁵.

Patients with post-Lyme disease complaints at least 12 months from initial treatment (N=40)

1. Age 18 or older.
2. Diagnosed with confirmed or probable Lyme disease fulfilling the case definition of Lyme disease by the CDC <https://www.cdc.gov/nndss/conditions/lyme-disease/case-definition/2017/>.
3. Received recommended antibiotic therapy for Lyme disease⁵ at least 12 months between the end of the initial antibiotic therapy and the xenodiagnostic procedure.
4. Persistent or recurrent symptoms that began or worsened within 6 months of the diagnosis and treatment for Lyme disease.

Acute EM (N=40)

1. Age 18 or older.
2. EM diagnosed by the study physician.
3. Receiving antibiotic therapy for Lyme disease for less than 48 hours.

Lyme Arthritis (N=40)

1. Age 18 or older.
2. Lyme arthritis⁵⁰ and have not received antibiotic therapy for the disease.

Healthy volunteers (N=20)

1. Age 18 or older.
2. No prior history of Lyme disease.
3. Negative whole cell enzyme-linked immunosorbent assay (ELISA) or C6-based antibody test for Lyme disease.

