For the other groups post-Lyme disease syndromes (PLDS), acute EM, and untreated Lyme arthritis, the precision with which the rates can be estimated from the observed data depends on the true underlying response rate and the sample size. Exact Clopper-Pearson 2-sided 95% CIs for the observed positivity rate the different proposed group sizes and a range of numbers of positive individuals are shown in Table 3. Healthy volunteers (negative controls) results will be used for specificity of the testing.

Table 3: Exact 95% Confidence Interval for the Observed Positivity Rate, for Varying Group Size (N) and Observed Numbers of Positive Individuals

# of observed positives samples	N=20	N=40
0	(0.000, 0.161)	(0.000, 0.09)
1	(0.009, 0.236)	(0.004, 0.13)

2	(0.0279, 0.301)	(0.014, 0.165)
5	(0.112, 0.468)	(0.054, 0.261)
10	(0.299, 0.701)	(0.142, 0.402)
15	(0.531, 0.888)	(0.242, 0.529)
20	(0.838, 1)	(0.352, 0.648)

Data will be collected for any positive tests by xenodiagnosis. Because there is no gold standard test among those we will employ, comparative positivity rates between the tests will be determined. Summaries of patient characteristics will be assessed by study group. For categorical variables, the numbers and proportions will be tabulated; for continuous variables, the mean, median, SD, and interquartile range will be reported. Fisher's exact test will be used to examine the association of 2 categorical variables. For continuous variables, t-tests and nonparametric methods, such as the Wilcoxon or Spearman's correlation coefficient, may be used to assess associations between subgroups of patients.

AEs related to xenodiagnosis will be tabulated and summaries with numbers and proportions will be given.

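### Objective 3 lists three overlapping time intervals with only unadjusted two-variable methods, and beyond 12 months from therapy time is confounded with symptoms in any analysis across Groups 1 and 2

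*Combined protocol and SAP*

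**What the plan says.** Section 2, Objective 3 asks for subject characteristics related to the likelihood of detection, including "time from infection, time between infection and therapy, time from therapy". No start or end point is given for any of the three. Elsewhere the documents use both anchors: Section 3.2 counts from the end of therapy, Section 4.5 from its start.

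The only analysis text is in Section 7.1. Fisher's "exact test will be used to examine the association of 2 categorical variables". For continuous variables, t-tests and nonparametric methods such as Wilcoxon or Spearman "may be used to assess associations between subgroups of patients". No regression, stratification or adjustment is named, and none of these methods is tied to Objective 3.

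Section 3.2 defines the treated groups (numbered as in Table 1):

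- Group 1 (N=100) has "at least 3 months and up to 12 months between the end of the therapy" and the procedure, with no symptom criterion.
- Group 2 (N=40) has "at least 12 months between the end of the initial antibiotic therapy and the xenodiagnostic procedure", with no upper limit, and must have "Persistent or recurrent symptoms that began or worsened within 6 months of the diagnosis and treatment for Lyme disease".

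Acute EM patients have had less than 48 hours of antibiotics at entry, and Lyme arthritis patients none. Both may later re-enrol, but only into Group 1.

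**The concern.** There are two separate problems.

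First, the intervals overlap. Time from infection contains delay to therapy and time from therapy. A two-variable test of it picks up whichever component matters and cannot say which.

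Second, the design leaves one cell empty: no asymptomatic treated patients are enrolled beyond 12 months. The study is powered on the hypothesis that symptoms and positivity go together, so symptom status is a confounder by the protocol's own reasoning. Any Objective 3 analysis that uses the full range of time from therapy must span Groups 1 and 2, and so compares a mixed group with a symptomatic one. A symptom effect could then be reported as an effect of time. Section 1 adds that symptoms seem to go with delayed therapy, so delay is exposed to the same problem.

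**Working it through.** **The plan's own figure.** Objective 3 has none. The only powered comparison is symptomatic against asymptomatic, and it supplies the rates used below. For 5% against 30%, two-sided 5%, 80% power and equal groups:

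- Uncorrected n per group = [1.96·√(2·0.175·0.825) + 0.8416·√(0.05·0.95 + 0.30·0.70)]² / 0.25² = 35.06.
- With continuity correction: (35.06/4)·[1 + √(1 + 4/(35.06·0.25))]² = 42.7, so 43 per group and 86 in total. This is the Table 2 entry. The other seven cells reproduce the same way.

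**Overlap of the intervals.** Time from infection = delay to therapy + course length + time from end of therapy. If one therapy date serves both intervals, course length drops out and the dependence is exact. If delay runs to the start and time from therapy runs from the end, only course length breaks it.

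The documents give no distributions, so assume time from therapy uniform over 3 to 12 months (variance 9²/12 = 6.75) and an independent exponential delay with mean and SD s months. Ignoring course length, the correlation of time from infection with time from therapy in Group 1 is √6.75 / √(6.75 + s²):

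| s (months) | 0.5 | 1 | 2 | 3 |
|---|---|---|---|---|
| correlation | 0.98 | 0.93 | 0.79 | 0.65 |

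**Delay against time from therapy.** In simulations of Group 1 alone, separate tests found the interval that truly mattered in about 79 to 86% of trials and the other in about 4 to 5%. These rest on an assumed strong effect (log-odds slope of 1 per SD). They show that the two can be separated, not that the trial has this power.

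**Time against symptoms.** Let f be the share of Group 1 that is symptomatic. Section 1 gives 10 to 40% of treated EM patients with symptoms at 12 months; the sample size assumes an equal split. With 5% and 30% positivity and no time effect, expected positivity is 0.05 + 0.25f in Group 1 and 0.30 in Group 2. The groups therefore differ although time does nothing.

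Simulation: 100 + 40 participants, no losses, two-sided Wilcoxon at 5% on time from therapy. Group 1 time was uniform over 3 to 12 months, and Group 2 time uniform from 12 to 36 or 120 months. Delay was lognormal with median 0.5 month, either unrelated to symptoms or doubled in symptomatic patients. Each f has four settings of 1,500 trials; trials with fewer than 3 positives in Group 1 were set aside.

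| f | Group 1 positivity | expected positives, Group 1 + Group 2 | unadjusted test significant, four settings | mean |
|---|---|---|---|---|
| 10% | 7.5% | 7.5 + 12 | 77.0, 76.0, 77.5, 76.0% | 76.6% |
| 25% | 11.25% | 11.25 + 12 | 58.3, 57.7, 57.6, 57.6% | 57.8% |
| 40% | 15% | 15 + 12 | 36.0, 35.4, 39.7, 33.7% | 36.2% |
| 50% | 17.5% | 17.5 + 12 | 24.9, 26.4, 24.7, 25.9% | 25.5% |

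A repeat run gave about 78% at f = 10% and 36% at f = 40%. The Group 2 upper limit cannot matter to a rank test, because every Group 2 time exceeds every Group 1 time. Differences between settings in a row are simulation error.

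**After adjustment.** A logistic model with symptom status, log delay and time from therapy (ordinary likelihood-ratio test) found time from therapy significant in 4.3 to 6.8% of trials for Groups 1 and 2 together and 4.7 to 7.3% in Group 1 alone.

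**Delay.** Where symptomatic patients were given twice the delay, and delay itself did nothing, the unadjusted test of delay across both groups was significant in 25 to 36% of trials.

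**The case against.** The strongest reply is that the plan does not commit to the faulty analysis. Section 7.1 lists general methods, some only as options, and summarises patient characteristics by study group. No text pools Groups 1 and 2 or puts acute EM or untreated arthritis into an analysis of time from therapy. Objective 3 asks for related characteristics, not independent effects, and it is unpowered. All of this stands. It means pooling is an inference, and the percentages describe what happens if it is done.

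Three stronger readings are tempting and are not supported:

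- A reader might infer that Objective 3 cannot tell which time matters. Within Group 1, delay and time from therapy vary separately and even separate tests distinguish them.
- A reader might infer that linear dependence invalidates the planned tests. It would defeat a joint model of all three intervals, which the plan does not propose. For two-variable tests it limits only how time from infection is read, and it is near-exact rather than exact if therapy has separate start and end dates.
- A reader might call an association with time from infection a false positive. That interval contains the other two, so the association is real; the error would be to treat it as a separate effect.

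Two features soften the design gap without closing it. Section 4.7 allows retesting after a positive result without meeting entry criteria, possibly beyond 12 months, but those people are selected on the outcome. Re-enrolment of EM and arthritis patients gives some before-and-after information, all within Group 1's window.

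The adjusted model will also be thin: with three terms, 7.5/3 = 2.5 to 17.5/3 = 5.8 expected positives per term.

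**Conclusion.** The point holds in limited form. Objective 3 has no defined interval endpoints, no analysis population and no adjustment. Time from infection cannot be interpreted apart from its two components. An unadjusted comparison across Groups 1 and 2 would report a time effect that is only a symptom effect in about 36% of trials at 40% symptomatic in Group 1 and about 78% at 10%, against about 5 to 7% after adjustment.

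These figures rest on the protocol's 5% and 30% rates, full enrolment, and every Group 2 participant counting as symptomatic. If the composite score of Section 7.1 classed some of Group 2 as asymptomatic, the confounding would be weaker. The correlations, and the figures for delay, rest on assumed distributions. The powered comparison of symptomatic with asymptomatic patients is not affected. This should be changed, but it does not threaten the trial's main question.

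**What to change.** Specify in the SAP for Objective 3:

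1. Define delay to therapy and time from end of therapy by named start and end dates.
2. In Group 1, fit both together with symptom status in one Firth-penalised or exact logistic model.
3. Report time from infection descriptively only.
4. For the effect of more than 12 months, compare Group 2 only with symptomatic Group 1, using the same composite score in both.
5. Keep acute EM and untreated arthritis out of the time-from-therapy analysis.
6. Label the whole analysis exploratory.

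The cost is wording and one model in place of separate tests, with no new visits, patients or samples. The price is precision. Group 1 is expected to yield about 7.5 to 17.5 positives, so intervals will be wide. The comparison in item 4 would have only about 10 to 40 of 100 Group 1 participants at 10 to 40% symptomatic. The simulation used ordinary logistic regression; the Firth and exact versions are proposed because positives are few and were not themselves simulated.
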